## Clinical Investigation Plan

### 1. LIST OF ABBREVIATIONS

AE	Adverse Event
ADE	Adverse Device Effect
CEC	Clinical Events Committee
CRF	Case Report Form
CRT-D	Cardiac Resynchronization Therapy Defibrillator
FDA	Food and Drug Administration
GCP	Good Clinical Practice
GFR	Glomerular Filtration Rate
HF	Heart Failure
HFH	Heart Failure Hospitalization
ICH	International Committee on Harmonization
IEC	Independent Ethics Committee
INR	International Normalized Ratio
IEC	Independent Ethics Committee
IV	Intravenous
LVEF	Left Ventricular Ejection Fraction
MedDRA	Medical Dictionary for Regulatory Activities
MI	Myocardial Infarction
NYHA	New York Heart Association
OPC	Objective Performance Criterion
PA	Pulmonary Artery
PMS	Post Market Study
PT	Prothrombin Time
PTT	Partial Thromboplastin Time
RHC	Right Heart Catheterization
RF	Radio Frequency
SADE	Serious Adverse Device Effect
SAE	Serious Adverse Event
SAP	Statistical Analysis Plan
SOP	Standard Operating Procedure

## Clinical Investigation Plan

### 2. PROTOCOL SYNOPSIS

Sponsor:	St. Jude Medical, Atlanta, GA
Protocol Title:	CardioMEMS HF System OUS Post Market Study
Document Control Number:	SJM-CIP-10147
Device:	The CardioMEMS™ HF System consists of a wireless, battery-less pressure sensor implanted into the pulmonary artery and an external electronics that powers and communicates with the sensor and transmits pulmonary artery pressure waveforms and measurements to a secure website for Investigator review and patient management.
Purpose:	The purpose of this Post Market Study (PMS) is to evaluate the use of the CardioMEMS™ HF System in patients with Class III Heart Failure in a real-world setting.
Objective:	The objective of this PMS is to confirm safety and effectiveness in a real-world setting.
Study Population:	
Adults with New York Heart Association (NYHA) Class III Heart Failure (HF) who have experienced a heart failure hospitalization within the past 12 months.
 
The patients will serve as their own historical controls for effectiveness (1 year prior to implantation).
 
All subjects who sign the informed consent form and satisfy the inclusion/exclusion criteria.
 
Ejection fraction data must be taken within the last 6 months or prior to implantation.

Study Design:	
This is a prospective, multi-center, open-label trial conducted in centers located outside of the United States (US).
 
All subjects who sign the informed consent form and satisfy the inclusion/exclusion criteria will be enrolled into the CardioMEMS™ HF System PMS and will be scheduled for follow-up visits at 1 month and every 6 months for 2 years.
 
Following sensor implant and hospital discharge, subjects will take PA pressure measurements on a daily basis, or as directed by the investigator. These measurements will be automatically transmitted to the secure patient database (Merlin.net website).

Timeline:	Study visits will be scheduled at Month 1, Month 6, and every 6 months thereafter for 2 years or until study termination.

*This confidential document is the property of Abbott and shall not be reproduced, distributed, disclosed or used without the express written consent of Abbott*

## Clinical Investigation Plan

Number of Subjects	Up to 800 subjects will be enrolled. Enrollment will be limited to 15% of the total study population at any one site.
Number of Sites:	This is a prospective, multi-center, open-label clinical trial to be conducted at up to 85 sites.
Safety Measures:	
Primary safety endpoints will be evaluated at 2 years: 1) freedom from device/system related complications and 2) freedom from pressure sensor failure.
 
Safety will also be assessed throughout the study by the frequency of Adverse Device Effects (ADEs), Serious Adverse Events (SAEs), and Serious Adverse Device Effects (SADEs).

Effectiveness Measures:	
The primary effectiveness endpoint is the annualized HF hospitalization rate at 1 year.
 
Supplemental analyses include mortality at 1 year, HF hospitalization or death at 1 year, patient compliance over the trial, training evaluation, and subgroup analyses.
 
Information regarding all hospitalization and deaths will be collected throughout the study.

Statistical Considerations:	
Primary Safety Endpoints            The primary safety hypotheses are that the device / system-related complication-free proportion of subjects will be at least 80% at 24 months (OPC used in the CHAMPION trial) and that the pressure sensor failure-free proportion of subjects will be at least 90% at 24 months (OPC used in the CHAMPION trial). Plotting and analysis of safety endpoints will also be displayed using Kaplan-Meier methods.            All safety analyses will be performed on the safety population.
 
Primary Effectiveness Endpoint            The primary effectiveness evaluation will compare the annualized HF hospitalization rate at 1 year compared to the HF hospitalization rate in the year prior to enrollment.            The effectiveness population consists of all subjects who received a sensor implant regardless of study completion status.
 
Supplemental Analyses            Mortality at 1 year will be analyzed. Plotting and analysis of mortality will be displayed using Kaplan-Meier methods.            The annualized HF hospitalization or death rate at 1 year in study will be compared to the HF hospitalization rate in the year prior to enrollment.

*This confidential document is the property of Abbott and shall not be reproduced, distributed, disclosed or used without the express written consent of Abbott*

## Clinical Investigation Plan

	
Patient compliance over the trial will be examined. The total number of PA pressure readings taken will be reported as a percentage of patient days at home.
 
Effectiveness analyses will be performed by the following subgroups: Women, Men, Reduced Ejection Fraction (< 40%), Preserved Ejection Fraction (<math>\geq 40\%</math>), Ischemic Etiology, Non-ischemic Etiology, With ICD/CRT-D, and Without ICD/CRT-D.
 
Frequency, purpose and outcome of all contacts made between site staff and implanted subjects post the implant visit will be examined.

Version:	C
Date:	18Apr2018

*This confidential document is the property of Abbott and shall not be reproduced, distributed, disclosed or used without the express written consent of Abbott*

## Clinical Investigation Plan

### 3. BACKGROUND AND RATIONALE

#### 3.1. Introduction

Heart failure (HF) is a clinical syndrome characterized by frequent hospitalization, poor quality of life, multiple comorbidities, high mortality and a complex therapeutic regimen. Affected individuals have a variety of symptoms such as dyspnea, fatigue, limited exercise tolerance, fluid retention, pulmonary congestion and peripheral edema. Patients suffer impairment in functional capacity and quality of life.

The incidence of HF is on the rise, affecting more than 5 million people in the US alone. Despite current guideline recommended therapies, rates of heart failure hospitalization remain high. Heart failure is the primary diagnosis in >1 million hospitalizations annually. Patients hospitalized for HF are at high risk for all-cause re-hospitalization, with a 1-month readmission rate of 25% (Go, et al., 2013).

#### 3.2. CHAMPION Trial Results

The CHAMPION trial demonstrated that management of heart failure using pulmonary artery pressure information obtained with the CardioMEMS HF System, in addition to traditional signs and symptoms, reduced HF hospitalizations.

The CHAMPION trial was conducted at 64 U.S. centers and enrolled 550 patients with NYHA Class III heart failure who had been hospitalized for heart failure in the previous year. All patients were implanted with a sensor and then randomized to Treatment (heart failure management on the basis of pulmonary artery pressure and standard of care) or Control (heart failure management on the basis of standard of care). CHAMPION met its primary endpoint of reduction in the rate of heart failure hospitalizations at 6 months with Treatment patients having 28% fewer heart failure hospitalizations compared to Control patients; benefit was sustained with a 37% reduction in heart failure hospitalizations over the full randomized study duration (Abraham, et al., 2011). All secondary endpoints were met with reduction in pulmonary artery pressures, reduction in proportion of patients hospitalized for heart failure, increase in days alive outside the hospital and improved quality of life.

The CardioMEMS™ HF System received CE Mark in 2011 and the current certificate was issued by BSI on May 1st 2014. The system received Food and Drug Administration (FDA) approval on May 28th 2014 for use in the United States.

#### 3.3. Indication for Use

The CardioMEMS™ HF System is indicated for wirelessly measuring and monitoring pulmonary artery (PA) pressure and heart rate in New York Heart Association (NYHA) Class III heart failure patients who have been hospitalized for heart failure in the previous year. The hemodynamic data are used by physicians for heart failure management and with the goal of reducing heart failure hospitalizations.

#### 3.4. CardioMEMS™ HF System

The CardioMEMS™ HF System provides pulmonary artery (PA) hemodynamic data used for the monitoring and management of heart failure (HF) patients. The system measures changes in PA pressure which physicians use to initiate or modify heart failure treatment.

[figure not shown]
The system includes the following components:

- Implantable wireless sensor with delivery catheter
- Patient or hospital electronics system
- Patient database (Merlin.net Website)

*This confidential document is the property of Abbott and shall not be reproduced, distributed, disclosed or used without the express written consent of Abbott*

## Clinical Investigation Plan

Figure 1. CardioMEMS HF System

The system provides the physician with the patient's PA pressure waveform including systolic, diastolic, and mean pressures as well as heart rate. The Sensor is permanently implanted into the distal PA using transcatheter techniques in the catheterization laboratory; the sensor baseline is set to the mean PA pressure using a pulmonary artery catheter. Daily PA hemodynamic measurements are taken by the patient in a supine position at home. The patient measurement system consists of an antenna and electronics unit that guides the patient through the short reading process. The data can be recorded from the home, hospital, physician's office, or clinic. The hemodynamic data is transmitted to the website which is accessible via a secure website to the patient's physician or nurse.

### Implantable Sensor

The sensor measures pulmonary artery pressure using MEMS (micro-electromechanical systems) technology and requires neither batteries nor leads. It is silicon wafer fabricated and measures 15 mm in length, 3.4 mm in width and 2 mm in thickness. The sensor is permanently implanted in a branch of the left or right pulmonary artery via a catheter. The Patient Electronics Unit provides both wireless communication and power to the sensor.

### Implantable Sensor Delivery System

*This confidential document is the property of Abbott and shall not be reproduced, distributed, disclosed or used without the express written consent of Abbott*

## Clinical Investigation Plan

The sensor is tethered to an over-the-wire delivery catheter. A right heart catheterization is performed, and a hand injected selective pulmonary angiogram is performed via the pulmonary artery catheter to define the distal pulmonary artery branch anatomy. A 0.018" guidewire is then advanced through the pulmonary artery catheter into the distal pulmonary artery. The pulmonary artery catheter is removed, and the delivery system is advanced over the guidewire. Once it is optimally positioned, the sensor is separated from the delivery system by releasing the tether wires and delivery system is then removed.

### Patient Electronics System

The electronics unit uses an antenna to transmit low power pulses of radiofrequency energy to power and communicate with the sensor. The electronics unit transmits the PA pressure information to the Merlin.net website.

### Merlin.net website

The Merlin.net website provides a secure user interface through a website for the clinician to review the PA pressure data from the CardioMEMS HF System.

## Clinical Investigation Plan

### **4. STUDY OBJECTIVE**

The objective of this Post Market Study is to provide safety and effectiveness data regarding the use of the CardioMEMS™ HF System in a commercial setting

### **5. STUDY DESIGN**

This is a prospective, multi-center, open-label clinical trial to be conducted up to 85 sites in centers located outside of the US.

Subjects who sign the informed consent form and meet the eligibility criteria at the Baseline visit will be eligible for the trial. Subjects will undergo the study-related procedures, including clinical laboratory measurements and body mass index (BMI) calculation. Note that for study related procedures/visits Investigator refers to the Principal Investigator or designee.

Eligible subjects will be scheduled for the Implant procedure (PA sensor implant in conjunction with a RHC procedure).

Subjects must also have an appropriately sized ( $\geq 7$ mm diameter) pulmonary artery branch identified by a selective pulmonary angiogram prior to Sensor implant. Subjects who do not meet this inclusion criteria will be documented as consented not implanted and will be followed for 30 days for safety.

Prior to hospital discharge, subjects will be trained on the home monitoring system and instructed to take pulmonary artery pressure measurements daily or as directed by their physician. Subjects will be supplied with a patient implant identification card, a Patient System Manual, and a Helpline phone number.

After discharge, the subject will take PA pressure measurements at home, as directed by the investigator, utilizing the CardioMEMS HF System. These measurements will be transmitted via modem to a secure data base. Patient compliance will be monitored by the sponsor and reported to the Investigator.

The Investigator or designee will review the PA pressure measurements transmitted from the home monitoring unit. Pressure thresholds are automatically set as described in Appendix C. These threshold notifications are intended to guide the Investigator to review the Merlin.net website. If the PA pressures are elevated or low, the Investigator or designee should make medication changes according to the guidelines in Appendix C. The Investigator or designee will review the PA pressure measurements on a weekly basis at a minimum and appropriately utilize the information obtained to assist in the clinical management of subjects. Weekly logins to the database will be monitored by the sponsor. Reminders will be sent to the clinical sites if there are no logins noted during the course of a 7 day window. Clinical and technical support will be available to the Investigator as needed.

- Follow-up study visits will be scheduled at Month 1, Month 6, and every 6 months thereafter for 2 years. Follow-up visits will include a physical exam, evaluation of NYHA Class (Appendix B), AE assessment, heart failure medications review, quality of life assessment, and assessment of any hospitalizations (including HF hospitalizations), that may have occurred between visits.

In addition, all contacts between site staff and study subjects post implant will be recorded on a log to capture frequency, purpose and outcome of each contact.

## Clinical Investigation Plan

### **6. STUDY POPULATION**

Study subjects must meet the following inclusion and none of the exclusion criteria to be eligible for the study.

#### **6.1. Inclusion Criteria**

1. Written informed consent obtained from subject
2.  $\geq 18$  years of age
3. Diagnosis of NYHA Class III Heart Failure
4. At least 1 HF hospitalization within 12 months of Baseline visit
5. Subjects with reduced LVEF heart failure should be receiving a beta blocker for 3 months and an ACE-I or ARB for one month unless in the investigator's opinion, the subject is intolerant to beta blockers, ACE-I or ARB.
6. Subjects with a BMI  $\leq 35$ . Subjects with BMI  $>35$  will require their chest circumference to be measured at the axillary level, if  $> 65$  inches the patient will not be eligible for the study.
7. Subjects with pulmonary artery branch diameter  $\geq 7\text{mm}$  - (implant target artery - assessed during the RHC)
8. Subjects willing and able to comply with the follow-up requirements of the study

#### **6.2. Exclusion Criteria**

1. Subjects with an active infection
2. Subjects with history of recurrent ( $> 1$ ) pulmonary embolism or deep vein thrombosis
3. Subjects who, in the Investigator's opinion, are unable to tolerate a right heart catheterization
4. Subjects who have had a major cardiovascular event (e.g., myocardial infarction, open heart surgery, stroke, etc.) within 2 months of Baseline Visit
5. Subjects with Cardiac Resynchronization Device (CRT) implanted  $< 3$  months prior to enrollment
6. Subjects with a Glomerular Filtration Rate (GFR)  $< 25 \text{ ml/min}$  (obtained within 2 weeks of the baseline visit) who are non-responsive to diuretic therapy or who are on chronic renal dialysis
7. Subjects with congenital heart disease or mechanical right heart valve(s)
8. Subjects likely to undergo heart transplantation or VAD within 6 months of baseline visit
9. Subjects with known coagulation disorders
10. Subjects with a hypersensitivity or allergy to aspirin, and/or clopidogrel (not applicable for subjects taking anti-coagulation therapy or other approved anti-platelets therapy).

## Clinical Investigation Plan

### **7. STUDY OR SITE TERMINATION**

The Sponsor or the Investigator has the right to discontinue the study at any time. As much as possible, this should occur after mutual consultation. The Investigator (or sponsor, where appropriate) is responsible for informing the Independent Ethics Committee (IEC) of trial closure.

Conditions may arise during the study that could prompt termination of the study or the study sites.

Conditions that may prompt such considerations include, but are not limited to, the following:

- The discovery of unexpected, serious, or unacceptable risk to the subjects enrolled in the study
- A decision on the part of Sponsor to suspend, discontinue, or shorten the study
- Study conduct at the study site may warrant termination under conditions that include the following:
  - Failure of Investigator(s) to enroll eligible subjects into the study
  - Failure of Investigator(s) to comply with regulations
  - Submission of false information from the research facility to Sponsor, the Clinical Monitor, or a regulatory authority
  - Insufficient adherence to protocol requirements
  - A conflict of interest of the Investigator, his/her institution, or site personnel that would negatively impact the integrity of the clinical trial
  - Institution or IEC under investigation

## Clinical Investigation Plan

### **8. STUDY PROCEDURES**

All subjects will be followed for 2 years. A subject is considered to have successfully completed the study upon completion of the 2 year visit (see Appendix A for the Schedule of Events).

#### **8.1. Screening Visit**

During the screening visit, the following procedures/assessments will be performed to determine subject eligibility:

- Informed Consent prior to the conduct of any study-related procedures
- Physical examination including vital signs (temperature, heart rate, blood pressure), weight, height, BMI calculation (refer to Appendix D)
- Medical and surgical history including ejection fraction data must be taken within the last 3 months to enroll in the study. If ejection fraction data is older than six months, ejection fraction data is required to be obtained at screening visit or prior to implantation.
- Patient history of all heart failure hospitalizations in the 12 months previous to the baseline visit as documented with information provided by the patient's cardiologist, internist, or referring physicians and review of all source documents of any heart failure hospitalizations reported in the previous year.
- Demographics
- NYHA Functional Classification
- Calculation of GFR (requires creatinine - refer to Appendix E)
- Assessment of medications
- Assessment of enrollment eligibility (inclusion/exclusion criteria)
- Completion of Quality of Life Questionnaire EQ-5D-5L

Eligible subjects will be scheduled for the Implant procedure. Subjects on anticoagulation therapy (e.g. warfarin) may be instructed by the Investigator to discontinue use 1-2 days prior to pressure sensor placement. The investigator should consider utilizing enoxaparin (Lovenox) per the site's standard of care as bridge therapy to Sensor placement in subjects who were on anticoagulation therapy.

For subjects at risk for gastro-intestinal bleeding during the period in which dual antiplatelet therapy is given, the investigator should consider a proton pump inhibitor such as omeprazole (Prilosec). Subjects at risk include the elderly, those with a history of gastroduodenal ulcers, GERD, esophagitis, intestinal polyps or cancer. Subjects who smoke or who are using steroids or non-steroidal anti-inflammatory drugs may also be at risk.

*This confidential document is the property of Abbott and shall not be reproduced, distributed, disclosed or used without the express written consent of Abbott*

## Clinical Investigation Plan

### 8.2. Right Heart Catheterization and Implant Procedure (Baseline Visit)

Before the RHC, the following procedures/assessments will be performed:

- Abbreviated physical examination (i.e., vital sign assessments and significant changes since Screening Visit) and weight
- Confirmation of enrollment eligibility (other than angiographic criteria)
- PT/PTT with International Normalized Ratio (INR) per institution standards for subjects previously on warfarin
- Assessment of heart failure medications
- Record any changes in medical history that occurred since screening visit.

The patient will then undergo a standard RHC. A selective, hand injected pulmonary angiogram will be performed via the pulmonary artery catheter to identify a suitable pulmonary artery branch for sensor implantation. Subjects must have an appropriately sized ( $\geq 7\text{mm}$  diameter) pulmonary artery branch. These procedures are considered standard of care for the sensor implant and are described in the User Manual. Subjects who do not meet this inclusion criterion will not receive the PA Sensor implant and will be considered ineligible for the study. These subjects will be documented as consented not implanted and will be followed for 30 days for safety. Patients with a suitable target pulmonary artery branch will undergo:

- Wireless implantable hemodynamic sensor implant
- Pulmonary artery catheter measurements (pulmonary systolic, pulmonary diastolic, heart rate, pulmonary mean, cardiac output) done 3 times consecutively with sensor measurements for setting of sensor baseline.
- Provide post-procedure vascular access site care per standard procedure
- At the Investigator's discretion, subjects should be discharged once stable with respect to the procedure and their heart failure.
- Please see User's Manual for implant details

Subjects who are currently on anticoagulant therapy (warfarin or other approved anticoagulants) will restart treatment. The subject's INR should be checked per the institutions standards. Those subjects not on chronic warfarin will be placed on aspirin and clopidogrel or other approved anti-platelet daily for 1 month starting on the day of Sensor placement. Any approved anticoagulant or anti-platelet therapy may be used as well. After 1 month, the subject will continue with aspirin therapy and clopidogrel (or other approved anti-platelet therapy) will be discontinued.

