## Clinical Investigation Plan

Implanted subjects will be evaluated at Month 1 ( $\pm$  7 days) and at Months 6, 12, 18, and 24 ( $\pm$  30 days) and the following procedures/assessments will be performed:

- Updated medical and surgical history
- Assessment of SAEs, ADEs, and SADEs that occurred since the last visit
- Reporting of any HF hospitalizations that have occurred since the last visit
- Abbreviated physical examination (significant changes since previous visit) including vital signs (heart rate, blood pressure), and weight
- Assessment of NYHA functional class
- Completion of Quality of Life Questionnaire EQ-5D-5L (6, 12, 18, and 24 month visits)
- Heart failure medication review
- PA pressure measurements may be obtained at the Investigator's discretion

Subjects will be reminded to obtain pulmonary artery pressure measurements utilizing the CardioMEMS HF System as directed. Subjects will be reminded of the current ACC/AHA guidelines or of the ESC guidelines regarding sodium and fluid restrictions.

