### 8.8. Deviations from CIP

A deviation is defined as an instance(s) of failure to follow, intentionally or unintentionally, the requirements of the CIP. The investigator should not deviate from the CIP.

In some cases, failure to comply with the CIP may be considered failure to protect the rights, safety and well-being of subjects; such non-compliance exposes subjects to unreasonable risks. Examples: failure to adhere to the inclusion/exclusion criteria, failure to report SAEs within given timeframe as per CIP, etc. Investigators should seek to minimize such risks by adhering to the CIP.

The PI must maintain accurate, complete, and current records, including documents showing the date of and reason for each deviation from the CIP. Relevant information for each deviation will be documented as soon as possible on the applicable CRF. The site will submit the CRF to the Sponsor.

The PI is required to adhere to local regulatory requirements for reporting deviations to the site IEC.

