## Clinical Investigation Plan

### 16. APPENDIX A: Schedule of Events

	Screening	Baseline (Implant)	Month 1	Months 6 and every 6 Months thereafter until Study Termination
Procedures	Prior to Implant	(within 30 days of Screening)	Visit 1 (30 ± 7 days)	Visits 2-5 or Study Termination (± 30 day window)
Informed Consent	X			
Demographics	X			
Past Medical & Surgical History. Ejection Fraction is part of this assessment and must be obtained within 3 months of the baseline visit or prior to implantation.	X			
Inclusion/Exclusion Criteria Review	X	X		
GFR (within 2 weeks of the implant procedure)	X			
INR (if indicated)		X		
Pulmonary artery measurement		X		
Physical Examination (including weight)	X 	X 	X 	X 
NYHA HF Classification	X		X	X
Pulmonary Artery Angiography		X		
Sensor Implant		X		
Sensor Measurements		X	X (Investigator discretion)	X (Investigator discretion)
Adverse Events Assessment		X	X	X
HF Hospitalizations	X		X	X
Quality of Life Assessment (EQ-5D-5L)	X			X (6, 12, 18, 24 months)
Medication Assessment (heart failure)	X	X	X	X
Subject Contact Log 			X	X

 Includes weight, height and vital signs (temperature, blood pressure, pulse, respirations).

 Includes weight, vital signs and significant changes from previous physical examination

 To be completed each time contact is made between the site staff and a study subject

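### Exclusion 10 and section 8.2 group subjects by different variables, so that on its most natural reading section 8.2 assigns aspirin to some subjects admitted despite an aspirin allergy

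*Combined protocol and SAP*

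**What the plan says.** **Section 6.2, exclusion 10.** Allergy or hypersensitivity to aspirin and/or clopidogrel excludes a subject, but the criterion is "not applicable for subjects taking anti-coagulation therapy or other approved anti-platelets therapy".

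**Section 8.2, anticoagulated subjects.** Warfarin and other anticoagulants are first treated as one group: "Subjects who are currently on anticoagulant therapy (warfarin or other approved anticoagulants) will restart treatment".

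**Section 8.2, month 1.** The anti-platelet regimen is then assigned by warfarin status alone: "Those subjects not on chronic warfarin will be placed on aspirin and clopidogrel or other approved anti-platelet daily for 1 month". The next sentence adds: "Any approved anticoagulant or anti-platelet therapy may be used as well".

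**Section 8.2, later treatment.** "After 1 month, the subject will continue with aspirin therapy and clopidogrel (or other approved anti-platelet therapy) will be discontinued".

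Section 8.2 contains no exception for allergic subjects. It refers to the User's Manual for implant details.

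**The concern.** The exemption in exclusion 10 means that the plan knowingly admits some subjects with an aspirin allergy. If section 8.2 is followed as it most naturally reads, some of those subjects are then assigned aspirin.

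This is a question of subject safety and of consistency between sites, not of statistical inference. With up to 85 sites, different readings are foreseeable. Section 8.8 is broad: "A deviation is defined as an instance(s) of failure to follow, intentionally or unintentionally, the requirements of the CIP". On the natural reading of section 8.2, an investigator who withholds aspirin from such a subject departs from the plan. The medication item at follow-up visits in section 8.3 is a "Heart failure medication review", and Appendix A is limited to heart failure drugs in the same way. The scheduled assessments are therefore not designed to show which reading a site has used.

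**Working it through.** No formula applies and the plan gives no figure to reproduce. The check sets the two sections side by side for a subject with an aspirin allergy.

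**Step 1: who is admitted, and who falls under the anti-platelet sentence.** In the last two columns, *strict* takes chronic warfarin literally, and *loose* takes it to stand for any anticoagulant.

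| Aspirin-allergic subject taking | Exclusion 10 | Anti-platelet sentence, strict | Anti-platelet sentence, loose |
|---|---|---|---|
| Chronic warfarin | admitted | no | no |
| Non-warfarin anticoagulant | admitted | yes | no |
| Another approved anti-platelet, no anticoagulant | admitted | yes | yes |
| None of these | excluded | not applicable | not applicable |

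The third row is inside both the exemption and the regimen group on either reading. The second row is inside both only on the strict reading. On that reading such a subject also falls under the restart sentence, and the plan does not say whether the anti-platelet instruction adds to it or replaces it.

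**Step 2: what month 1 requires.** The regimen wording can be parsed in two ways:

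- aspirin, plus either clopidogrel or another agent; or
- either the aspirin-clopidogrel pair, or another agent alone.

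Two other places favour the first. Section 8.1 describes the early period as one of dual antiplatelet treatment. The sentence on later treatment attaches the alternative to clopidogrel only and names aspirin without one. On the first parse, and if *as well* means in addition, the subject receives aspirin in month 1. A clopidogrel-only allergy does not raise the same problem, because the text offers an alternative to clopidogrel.

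**Step 3: what happens after month 1.** The sentence keeps aspirin and stops clopidogrel or its alternative. Taken at face value, for a subject in the third row it keeps the drug to which the subject is allergic and stops the kind of agent on which the exemption rested. It states no exception.

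**Step 4: the alternative readings, for a subject in the third row.**

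| Reading | Month 1 | After month 1 |
|---|---|---|
| First parse, *as well* = in addition | aspirin assigned | aspirin continued, other agent stopped |
| Second parse | can be free of aspirin | face value: aspirin named; if *continue* covers only current aspirin users: no instruction |
| *As well* = instead | can be free of aspirin | as in the row above |

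None of these readings gives the subject a stated instruction for the whole period that takes account of the allergy.

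**Step 5: reach into the analyses.** Section 9.1.1 counts only events at least possibly related to the sensor or the external electronics. Section 9.1.2 counts only sensors that give no readings. The primary effectiveness endpoint is the HF hospitalization rate. A reaction to aspirin would not ordinarily enter any of these, and the sample size calculations do not depend on the regimen.

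**The case against.** The strongest reply is that the two sections can be read together. Section 8.2 opens by grouping warfarin with other anticoagulants, so the chronic-warfarin wording that follows may simply mean the subjects who are not anticoagulated. The *as well* sentence names the same two drug classes as the exemption, which suggests that it was meant to let exempted subjects stay on their own drug. The exemption itself makes sense only if they need not take the drug to which they are allergic. The User's Manual may also settle the matter, and investigators may avoid aspirin on their own judgement.

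Much of this stands. It removes subjects on a non-warfarin anticoagulant from the conflict if the loose reading is accepted, and it makes an aspirin-free month 1 possible. It does not take subjects on another anti-platelet out of the regimen group, and it supplies no instruction for them after month 1.

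A reader might infer two stronger claims that the documents do not support:

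- *No reading avoids aspirin after month 1.* The verb *continue* can be limited to subjects already taking aspirin. The text is then silent for the allergic subject and assigns nothing.
- *Subjects on chronic warfarin are also assigned aspirin*, because the last sentence says *the subject* without naming a group. This is strained, since section 8.2 never starts aspirin for them. The scope of the phrase is still worth clarifying.

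On detectability, Appendix F includes medications among source-document content, and section 13.5 provides for source data verification. A site's practice could therefore be traced through source review, although not through the scheduled medication assessments. Whether withholding aspirin is a deviation depends on the same disputed reading, so section 8.8 is a consequence of the problem and not separate evidence for it.

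**Conclusion.** The mismatch in grouping is certain from the text: one section uses any anticoagulant or another anti-platelet, the other uses chronic warfarin, and section 8.2 writes no allergy exception. That this assigns aspirin to some exempted aspirin-allergic subjects is the most natural reading but not the only one. The conflict is clearest for subjects admitted because they take another anti-platelet, and conditional on a strict reading of the warfarin wording for those on a non-warfarin anticoagulant. Under the alternative readings, the fault becomes the lack of a clear instruction after month 1.

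The size cannot be given. The documents do not say how many subjects have an aspirin allergy or enter under the exemption, and none is estimated here. The effect in practice also depends on the User's Manual, which is not among the documents. No effect on the primary analyses, sample size or power is expected. The text should be corrected because it bears on subject safety and the correction is small.

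**What to change.** Reconcile exclusion 10 with section 8.2:

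1. Use the same group definitions in both places, and say whether the warfarin wording means warfarin only or any anticoagulant.
2. For each group, including subjects exempted despite an allergy, state which instruction applies during month 1 and which applies afterwards.
3. Make the and/or structure of the month 1 regimen explicit, and say whether *as well* means in addition or instead.
4. Say which subjects *the subject* covers in the sentence on treatment after month 1.
5. If the User's Manual already settles these points, cite it for them in section 8.2.

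The clinical content of each instruction is for the sponsor's clinical team, and no regimen is proposed here. The cost is amended wording in two places and a notice to sites, with no change to sample size, power or analysis.
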